## 2.3 Study Subjects

Demographic endpoints and subject characteristics will be summarized using descriptive statistics overall based on the MITT population using observed cases. There are no planned inferential statistical analyses of demographic endpoints or subject characteristics.

### 2.3.1 Subject Disposition

The number of subjects screened will be shown in total.

The number of subjects in each study population (i.e., MITT, and Safety) will be summarized by country and in total.

The disposition of subjects will be presented by country and in total, including numbers of subjects who were completed and withdrawn (including primary reason for withdrawal).

The number of subjects expected, completed, withdrawn, and missed will be summarized by scheduled visit, using the following definitions:

- Expected = all subjects at screening minus subjects who have withdrawn up to that visit.
- Completed = subjects who showed up at that visit.
- Withdrawn = all subjects who have withdrawn up to that visit (cumulative).
- Missed = expected subjects minus completed subjects.

All withdrawn subjects will be listed individually, including at least subject number, date and reason for withdrawal, and last visit performed.

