#### 3.5 Procedures/Reasons for Subject Discontinuation

An investigator may decide to discontinue a subject from the clinical study for safety reasons. Although the importance of completing the entire clinical study should be explained to the subject by the clinical study personnel, any subject is free to discontinue participation in this clinical study at any

time and for whatever reason, specified or unspecified, and without any prejudice. No constraints are to be imposed on the subject, and when appropriate, a subject may be treated with other conventional therapy when clinically indicated.

When a subject does not complete the clinical study, he/she will be fully assessed, if such assessment is possible. The procedures designated for the closest upcoming study visit should be completed for a subject discontinuing the clinical study and the appropriate eCRF should be completed.

All discontinuations and the reason for discontinuation are to be documented by the investigator on the Study Exit form.

For discontinuation due to an AE, the AE form is to be completed. The investigator should also ensure that the subject receives suitable therapy for the AE.

A subject who has been enrolled cannot be replaced by another subject if he/she discontinues the clinical study for any reason.

Pregnancies occurring during the screening period are considered as screening failures; they should be recorded as such in the electronic case report form (eCRF) and no pregnancy form is to be completed.

In case of a pregnancy occurring after the baseline visit, follow the procedures described in Section 7.1.6. The subject may remain in the study, but no invasive procedure should be conducted.

The sponsor may also decide to prematurely terminate or suspend a subject's participation in the clinical study.

Potential reasons for discontinuation are defined below:

The withdrawal criteria are:

- **Medical Reasons** If the subject suffers from a medical condition and/or Adverse Events that, in the judgment of the investigator makes it medically necessary to withdraw the subject. The specific rationale for investigator-initiated withdrawal of a subject for medical reasons should document the specific condition for withdrawing the subject.

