- **Withdrawal by Subject:** Includes consent withdrawal, subject relocation, schedule conflicts. A subject can withdraw their consent to participate in the study at their own request or be withdrawn from participation in the study at the request of their legally authorized representative at any time for any reason.
- **Lost to follow-up:** If a subject does not return for a scheduled visit, reasonable effort shall be made to contact that subject, confirm with three documented phone calls and a certified letter (delivery receipt requested) without answer before declaring the subject lost to follow-up.

- **Other:**

This category is to be used for a subject who discontinues due to a reason other than as specified in the pre-defined categories above. Explain the reason for discontinuation.

If reason for discontinuation is “withdrawal by subject” or “other”, the subject will be questioned to rule out the possibility of an AE. If the AE led to discontinuation then “adverse event” should be chosen as the reason for discontinuation, rather than “withdrawal by subject” or “other”.

If an AE which, according to the investigator’s assessment, is related to the use of any of the study products and is still ongoing at the time of the withdrawal, the investigator shall follow-up the subject until the AE resolves, is assessed by the investigator to be “chronic” or “stable” or subject is lost to follow up. Follow-up information shall be reported on the AE follow-up form.

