#### 4.4 Subject Identification Number

Prior to any study procedures being conducted, the subject must sign the informed consent form (ICF). Each subject who has signed the ICF will be assigned a screening number. Upon enrollment, each subject will be assigned a subject number that will be allocated in ascending order within each center. A screen failure is a subject who signed the informed consent but never enrolled (i.e. received treatment) in the study. For screen failures, the subject source documents should indicate which assessments have been made and the reason why the subject was determined to be a screen failure. A screen failure should not be re-entered in the study. A subject is considered enrolled when they have signed the ICF and been treated.

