#### 10.4.1 Data Entry and Collection

A 21 Code of Federal Regulations Part 11-compliant electronic data capture application will be used to collect, modify, maintain, archive, retrieve, and transmit study data created in US. The international standard for clinical study of medical devices for human subjects, ISO14155:2011, CCI as well as The International Conference on Harmonization (ICH) Guideline for GCP (E6), as applicable for medical device. An eCRF is required and should be completed electronically for each screen failure as well as enrolled subjects.

The eCRF includes password protection and internal quality checks, such as automatic range checks, to identify data that appear inconsistent, incomplete, or inaccurate. Study data should be entered directly from the source documents, which are to be defined at each site before inclusion of the first subject.

Authorized study site personnel designated by the investigator should complete data collection. Appropriate training and security measures should be completed with all authorized investigation site personnel prior to the study being initiated and any data being entered into the system for any subject.

The study data is the sole property of the sponsor and should not be made available in any form to third parties, except for authorized representatives, without written permission from the sponsor. At the end of the study, electronic data are kept at the sponsor and a copy (provided by the vendor) at the study site as part of the investigator file.

Any delegation of collection of data should be specified in a signature and delegation log.

All data shall be entered in English. The eCRFs should always reflect the latest observations on the subjects participating in the study. Therefore, the eCRFs shall be completed as soon as possible during or after the subject's visit. The subject's identity must always remain confidential, i.e. the name and address of the subjects must not be registered in the eCRFs or in the database. The investigator must verify that all data entries in the eCRFs are accurate and correct. If some assessments are not done, or if certain information is not available, not applicable or unknown, the investigator shall indicate this in the eCRF. The investigator shall electronically sign off the study data. By signing, the investigator takes responsibility for the accuracy, completeness, and legibility of the data reported to the sponsor in the eCRF.

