#### 2.1.1 Programming Conventions

EMB Statistical Solutions will have responsibility for performing analyses. All computations for statistical analyses will be performed using SAS® software, Version 9.4 or later. All SAS programs used in the production of statistical summary outputs will be validated with independent programming prior to finalization. In addition, all program outputs will be independently reviewed. The validation process will be used to confirm that all data manipulations and calculations were accurately done. Once validation is complete, a senior statistical reviewer will perform a final review of the documents to ensure the accuracy and consistency with this plan and consistency

GALDERMA EST. 1981	Title 05DF2007 Statistical Analysis Plan (SAP)	CC I [REDACTED]
-----------------------	--	--------------------

within tables. Upon completion of validation and quality review procedures, all documentation will be collected and filed by the project statistician or designee.

The electronic case report form (eCRF) data for all subjects will be provided in Standard Data Tabulation Model (SDTM) datasets. Analysis Data Model (ADaM) datasets will be developed from the SDTM datasets for use in table and figure production.

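### The SAP's visit-attendance table counts Expected from everyone screened, so untreated screen failures appear as Missed (or Withdrawn) at follow-up visits

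*SAP*

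**What the plan says.** SAP section 2.3.1 (Subject Disposition) plans a table of subjects expected, completed, withdrawn and missed at each scheduled visit. Its base is given as "Expected = all subjects at screening minus subjects who have withdrawn up to that visit", and the shortfall as "Missed = expected subjects minus completed subjects". Completed means attending the visit, and Withdrawn is cumulative. Screen failures are not mentioned in these definitions.

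Protocol section 4.4 separates the two groups: "A screen failure is a subject who signed the informed consent but never enrolled (i.e. received treatment) in the study", whereas "A subject is considered enrolled when they have signed the ICF and been treated".

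Protocol section 3.5 lists the reasons for discontinuation. Screen failure is not among them. The section does say, for one case, "Pregnancies occurring during the screening period are considered as screening failures; they should be recorded as such". The nearest withdrawal category is the residual Other: "This category is to be used for a subject who discontinues due to a reason other than as specified in the pre-defined categories above".

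Screen failures will also be in the data. Protocol section 10.4.1 states "An eCRF is required and should be completed electronically for each screen failure as well as enrolled subjects", and SAP section 2.1.1 states "The electronic case report form (eCRF) data for all subjects will be provided in Standard Data Tabulation Model (SDTM) datasets".

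**The concern.** The definition starts from the screened set and subtracts only withdrawals. A person who consented, failed screening and was never treated is therefore still expected at Week 2, Week 4 and so on to Week 48. That person cannot attend, so the formula records a missed visit each time. If a site or programmer codes the screen failure as a withdrawal, Missed is right but the cumulative Withdrawn count includes someone who never entered follow-up.

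The attendance table is where a reader checks completeness of follow-up. That check matters here because the effectiveness analyses rest on observed cases (SAP section 2.4.2). A table that reports missed visits or withdrawals for untreated people understates how complete follow-up was.

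**Working it through.** The plan gives no figure to reproduce, so the check applies the SAP's four definitions directly.

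**Inputs**
- Treated subjects: n = 50, the approximate enrolment in the protocol synopsis and SAP section 1.1.2.
- Main follow-up visits: Visits 3 to 10, that is 8 visits (Weeks 2, 4, 8, 16, 24, 32, 40 and 48). Visits 4a and 4b are left out because they are scheduled only after a touch-up.
- Screen failures: s, an assumption (0, 5, 10 or 20), because the documents give no count or rate. Of these, m are not coded as withdrawn.
- For the main illustration: all treated subjects attend and none withdraws.

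**Formulas at each of Visits 3 to 10**
- Withdrawn = s − m
- Expected = (50 + s) − (s − m) = 50 + m
- Completed = 50
- Missed = (50 + m) − 50 = m

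The true values are Missed = 0 and Withdrawn = 0, so the two excesses always add up to m + (s − m) = s.

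**No screen failure coded as withdrawn (m = s)**

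| s (assumed) | Expected | Missed per visit | Apparent attendance | Falsely missed visits, 8 × s |
|---|---|---|---|---|
| 0 | 50 | 0 | 50/50 = 100% | 0 |
| 5 | 55 | 5 | 50/55 = 90.9% | 40 |
| 10 | 60 | 10 | 50/60 = 83.3% | 80 |
| 20 | 70 | 20 | 50/70 = 71.4% | 160 |

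**All coded as withdrawn (m = 0).** Missed = 0, which is correct, but Withdrawn = 0, 5, 10 or 20 against a true 0.

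**With some real loss.** Assume 3 treated subjects have withdrawn, 45 attend, and there are 12 screen failures (62 screened).
- Treated base: Expected = 50 − 3 = 47 and Missed = 47 − 45 = 2, or 2/47 = 4.3%.
- SAP wording, screen failures not coded as withdrawn: Expected = 62 − 3 = 59 and Missed = 59 − 45 = 14, or 14/59 = 23.7%.
- SAP wording, screen failures coded as withdrawn: Missed = 2, but Withdrawn = 3 + 12 = 15 against a true 3.

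**The case against.** The strongest reply is that the intended meaning is clear and the literal reading is unlikely to be programmed.
- SAP section 2.2 bases the analyses on the MITT and Safety populations, both limited to treated subjects.
- Protocol section 4.4 assigns a subject number only on enrolment. A screen failure has no subject number and no follow-up visit scheduled.
- SAP section 2.1.1 says tables are built from ADaM datasets, whose subject set is not described. A record in SDTM does not by itself put a screen failure in this table.
- The table shells are in a companion document (SAP section 2.1.2) that is not available here and may already fix the set.
- A reader could spot the mismatch from the screened total and the MITT and Safety counts in the same section.

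These points are fair evidence of intent, and they keep the matter minor. They do not change the definition. Section 2.3.1 also reports the screened total, so it is not confined to the two analysis populations, and it names its own base without using the term enrolled, which the protocol defines. A shell with a treated base would contradict the SAP text.

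One part of the reply has more force. The Withdrawn route is the weaker of the two: the SAP lists withdrawn subjects by subject number, which screen failures lack, and only the residual Other category would admit them. Missed is thus the more literal outcome, and excess Withdrawn arises only if sites or programmers code screen failures that way.

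**Conclusion.** The definition is wrong as written. Followed exactly, it adds one to Missed, or to Withdrawn if so coded, for each screen failure at every main follow-up visit. The error is zero only if there are no screen failures. Its actual size is unknown, because every screen-failure count used here is an assumption, and the attendance percentages also assume 50 treated subjects with full attendance.

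Severity is minor. The effect is confined to one descriptive table. Effectiveness uses observed cases in the MITT population and safety uses the Safety population, so neither is touched. Confidence is moderate, since the unseen shells may already apply a treated base.

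**What to change.** Reword SAP section 2.3.1 so that, from Visit 2 (baseline) onward, Expected is the number of treated (enrolled) subjects minus those withdrawn up to that visit, with Completed, Withdrawn and Missed counted in the same treated set. Report the number screened and the number of screen failures separately.

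Check with an assumed 10 screen failures, 50 treated subjects, full attendance and no withdrawals: screened 60 and screen failures 10 are shown on their own, and each visit from Visit 2 gives Expected 50, Completed 50, Missed 0, Withdrawn 0. This holds even if some subjects fail screening at Visit 2, because their attendance is not counted in Completed and Missed cannot become negative.

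The cost is two sentences. Under SAP section 2.1, that is a SAP amendment if made before database lock, or a note in the clinical study report afterwards. The attendance rows would start at Visit 2, and Visit 1 attendance would appear only through the screened and screen-failure counts.

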**CLINICAL STUDY FLOW CHART****Figure 1: Study Flow Chart**

## SCHE DULE OF EVENTS

Table 1: Schedule of Events

	Visit 1 Day 1 to Day 1	Visit 2 Day 1	Visit 3 Week 2 (± 3 Days)	Visit 4 Week 4 (± 3 Days)	Visit 4a 2 Weeks after touch-up (± 3 Days)	Visit 4b 4 Weeks after touch-up (± 3 Days)	Visits 5-9 Weeks 8-40 after baseline OR touch-up (± 5 Days)	Visit 10 or ET
Screening	Baseline / Tx	Follow-up	Follow-up / Touch-up	Follow-up	Follow-up	Follow-up	Follow-up	Follow-up
PROCEDURE								
Informed consent	X							
Medical history	X	X 						
Demographics	X							
Inclusion/exclusion	X	X 		X 				
Urine pregnancy test 	X	X 	X 	X 				
Treatment or touch-up		X		X 				
MLFS (investigator)	X	X 	X 	X 				
WAS upper perioral lines & oral commissures (investigator if applicable) 	X	X 		X 				
GAIS (subject and investigator)					X	X	X	X
Evaluate device deficiencies		X 		X 				
Photography		X 		X 				
Concomitant meds/procedures	X	X 	X	X 	X	X	X	X
Assessment of AEs	X	X 	X	X 	X	X	X	X

Abbreviations: GAIS, Global Aesthetic Improvement Scale; MLFS, Medicis Lip Fullness Scale; WAS, Wrinkle Assessment Scale

 Omit if the screening and baseline visits occur on Day 1 Prior to treatment Post treatment Omit if touch-up was not performed For females of childbearing potential Optional touch-up at Visit 4 to obtain optimal aesthetic improvement.  
*If a touch-up is performed, a 2wk and 4wk follow-up visits are scheduled (Visits 4a & 4b)* Subjects who are not treated in the upper perioral area or the right & left oral commissures at baseline (i.e. treated in the upper and lower lips only) are not required to have WAS assessed beyond

14(80)

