### 3.4.4 Visit 4: Week 4 ( $+3$ days)

- Interview and assess for AEs.
- Interview for concomitant medications/procedures.

CCI

- Obtain photography (if an optional touch up will be performed, ensure photos are taken prior to treatment).

CCI

- Investigator assessment of lip fullness using the MLFS.
- For subjects in the US: Investigator assessment of perioral rhytid wrinkle severity using the WAS.
- Assess whether optimal aesthetic improvement has been obtained (as agreed by the investigator and subject). If touch-up is to be performed, confirm eligibility criteria. No touch-up should be given if the subject has a disease or condition described in the exclusion criteria, or an ongoing treatment-related AE that in the opinion of the investigator would be worsened by touch-up treatment. If needed, re-schedule for touch-up treatment within the visit window.
- If subject does not receive touch-up treatment, schedule the Week 8 visit (Visit 5).

The following procedures should be completed if touch-up treatment is performed:

- Perform UPT for females of childbearing potential.
- Investigator to perform optional touch-up treatment with *Restylane Kysse* (upper and lower lips, and perioral rhytids, if treated at baseline).
- Evaluate the subject for post-treatment AEs.
- Record post-treatment concomitant medications/procedures
- Evaluate for device deficiencies.

CCI

- Schedule the 2 weeks after touch-up visit (Visit 4a).

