#### **3.4.5 Visit 4a: 2 Weeks After Touch-up ( $\pm 3$ days)**

This visit should only be conducted for subjects who received a touch-up treatment at Visit 4.

- Interview and assess for AEs.
- Interview for concomitant medications/procedures.

CCI

- Obtain photography.
- Schedule the 4 weeks after touch-up visit (Visit 4b).

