#### 1.1.1 Study Design

This is a prospective, open-label, multi-center study to evaluate the safety and effectiveness of *Restylane Kysse* for lip augmentation and correction of perioral rhytids, if applicable, in subjects with both biological parents of full Chinese descent.

Approximately 50 subjects with a score of 1 (Very Thin) or 2 (Thin) on the Medicis Lip Fullness Scale (MLFS) will be enrolled. The upper lip and lower lip scores do not have to be equal as long as each score is either 1 or 2 at baseline.

Following the informed consent and screening process, eligible subjects will be injected in the lips by the investigator at baseline. The method of injection is at the discretion of the investigator and will be recorded. Sufficient amount of product should be injected to achieve optimal aesthetic improvement as determined by the investigator and subject. Optimal aesthetic improvement is defined as at least 1-point improvement from baseline using the MLFS and the best correction that can be achieved as agreed by the investigator and the subject.

Subjects in the US meeting the Wrinkle Assessment Scale (WAS) inclusion criteria may also receive optional treatment with *Restylane Kysse* in the perioral rhytids at baseline. Treatment of the upper perioral lines, vermillion border, philtral columns, Cupid’s bow, and/or oral commissures may be performed to obtain optimal aesthetic improvement, as agreed by the investigator and subject.

Touch-up treatment of the lips and perioral area, if treated at baseline, may be administered 4 weeks after baseline treatment if deemed necessary to obtain optimal aesthetic improvement; this decision should be agreed upon by the investigator and the subject. Touch-up treatment will not be performed if the subject has a disease or condition described in the exclusion criteria or is experiencing an ongoing treatment-related AE that, in the opinion of the investigator, would be worsened by touch-up treatment.

The recommended maximum injected volume per subject per treatment visit is 6 mL (i.e. 1.5 mL for the upper lip, 1.5 mL for the lower lip, and 3 mL for perioral area, if treated). Treatment will be performed according to the approved Instructions for Use (IFU).

Subjects will have in-clinic follow up visits at 2, 4, 8, 16, 24, 32, 40, and 48 weeks after the last injection. If a touch-up is deemed necessary and performed at 4 weeks post-baseline, a second 2-week and 4-week follow-up visits should be scheduled.

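### If Visits 4a and 4b are tabulated under the single Expected rule in SAP 2.3.1, every non-withdrawn subject without a touch-up is counted as having missed them

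*SAP*

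**What the plan says.** SAP 2.3.1 introduces the attendance table as follows: "The number of subjects expected, completed, withdrawn, and missed will be summarized by scheduled visit, using the following definitions". Three of its definitions matter here:

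- "Expected = all subjects at screening minus subjects who have withdrawn up to that visit"
- "Completed = subjects who showed up at that visit"
- "Missed = expected subjects minus completed subjects"

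The fourth, Withdrawn, is cumulative. None of the definitions refers to touch-up. The section does not list the visits that form the rows, and it sets no visit apart.

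On Visit 4a, protocol 3.4.5 states: "This visit should only be conducted for subjects who received a touch-up treatment at Visit 4". Protocol 3.4.6 places the same restriction on Visit 4b. Under protocol 3.4.4, a subject without a touch-up goes from Visit 4 directly to Visit 5. Touch-up is optional in both documents, and neither gives an expected rate.

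The protocol's Schedule of Events (Table 1) gives 4a and 4b a column each, and its note 6 describes them as scheduled when a touch-up is done. SAP 1.1.1 likewise says that after a touch-up "a second 2-week and 4-week follow-up visits should be scheduled".

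**The concern.** The Expected definition suits visits that every treated subject is due to attend. Visits 4a and 4b are not of that kind. Only touch-up recipients can appear as Completed there, but Expected contains everyone who has not withdrawn. The difference between the two, reported as Missed, would then consist mainly or wholly of subjects whom the protocol never asked to come.

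These two visits carry the adverse-event interviews 2 and 4 weeks after re-injection, in a study with a stated safety objective. The by-visit table is the SAP's summary of how complete follow-up was. On these two rows it could suggest widespread non-attendance where there was none, and a real gap in post-touch-up follow-up would be pooled with subjects who were never due.

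**Working it through.** The plan states no figure to reproduce, so the check applies the SAP definitions literally.

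**Inputs.**
- S, subjects at screening, and W, subjects withdrawn by the visit: the terms of Expected in SAP 2.3.1.
- T, touch-up recipients not withdrawn by the visit: the only subjects due at 4a and 4b (protocol 3.4.5 and 3.4.6).
- N, treated subjects: about 50 planned (SAP 2.7).
- Touch-up rate: not in the documents, so varied from 0% to 100%.

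**Rule as written, all those due attending.**
- Expected = S − W
- Completed = T
- Missed = S − W − T

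The true number missed is T − T = 0.

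**Base case.** S = N = 50 (no screen failures), W = 0. The result is the same at each of Visits 4a and 4b.

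| Assumed touch-up rate | Expected | Completed | Missed under SAP 2.3.1 | Truly missed |
|---|---|---|---|---|
| 0% | 50 | 0 | 50 (100%) | 0 |
| 20% | 50 | 10 | 50 − 10 = 40 (80%) | 0 |
| 40% | 50 | 20 | 50 − 20 = 30 (60%) | 0 |
| 60% | 50 | 30 | 50 − 30 = 20 (40%) | 0 |
| 80% | 50 | 40 | 50 − 40 = 10 (20%) | 0 |
| 100% | 50 | 50 | 0 | 0 |

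**With withdrawals.** Assume W = 3 and a 40% touch-up rate. Expected = 50 − 3 = 47. Completed = 0.40 × 47 = 18.8, rounded to 19. Missed = 47 − 19 = 28, and 28/47 = 59.6%. Withdrawn subjects leave Expected, so the miscount covers non-withdrawn subjects without a touch-up, not all subjects without one.

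**Separate from screen failures.** Missed can be split as (S − N) + (N − W − T). The first term is the number of screen failures, if they are not treated as withdrawn; SAP 2.3.1 does not say. The second is the touch-up error. Assume S = 60, N = 50, W = 0 and a 40% rate: Missed = 10 + 30 = 40, or 40/60 = 66.7%. Starting from treated subjects removes the 10 but leaves the 30.

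**What the Missed cell can show.** If m of the T subjects due do not attend, Completed = T − m and Missed = S − W − (T − m). The cell depends only on T − m. With S = 50 and W = 0, 20 touch-ups with none absent gives 50 − 20 = 30, and 30 touch-ups with 10 absent gives 50 − (30 − 10) = 30. The cell is the same, while the true number missed is 0 in one case and 10 in the other.

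**After the change.** With Expected = T, Missed = T − (T − m) = m at any touch-up rate: 0 and 10 in those two cases.

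**The case against.** The strongest reply is that SAP 2.3.1 names no rows. Visits 4a and 4b come into being only when a touch-up is given, so for anyone else they are arguably not scheduled visits at all. Table formats are in a companion document (SAP 2.1.2) that is not available here. A format that omits these visits, or uses touch-up recipients as the denominator, would avoid the problem. This stands as a limit: a reader might infer that the report is certain to show the false count, and the documents do not establish that. It does not remove the point. Table 1 gives both visits columns, so including them is the natural reading. The companion document is assigned formats, while the counting definitions are in SAP 2.3.1 and carry no condition.

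A reader might also infer that a real missed post-touch-up visit would be untraceable. That goes too far, because only the Missed cell is uninformative. Completed remains correct at 4a and 4b. Treatment administration is summarised by treatment session (SAP 2.5.1), which should show how many subjects had a touch-up. Subject data are listed (SAP 2.1.2), and withdrawals are listed with the last visit performed.

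Nor do the documents support reading this as a threat to the results. Effectiveness endpoints start at Week 8 after last injection (SAP 1.4) and use observed cases in the MITT population (SAP 2.4.2). Adverse-event summaries count subjects and events in the Safety population (SAP 2.2.2 and 2.5.2) and do not use Expected. Adverse events are also asked about at every visit (protocol 7.1.1.2), so Visit 5 covers the period after a touch-up too.

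Finally, the Missed formula itself is sound. The fault is in the Expected definition that feeds it, which also raises the screen-failure question. One edit can settle both.

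**Conclusion.** The point holds in a limited form. SAP 2.3.1 applies one Expected definition to every scheduled visit, and that definition does not fit two visits that the protocol reserves for touch-up recipients. If 4a and 4b are rows of the table, Missed there equals the number of non-withdrawn subjects without a touch-up, plus any real absences and any screen failures left in the base. With 50 treated subjects, no screen failures or withdrawals and full attendance of those due, the false count runs from 40 (80%) at a 20% touch-up rate to 10 (20%) at 80%, and disappears only at 100%. These rates are assumptions.

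The consequence is a misleading cell in one descriptive table. It is worth correcting because the correction is cheap and the visits concern safety follow-up, but it is minor and leaves the study's conclusions unaffected.

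**What to change.** In SAP 2.3.1, define Expected at Visits 4a and 4b as subjects who received a touch-up minus those withdrawn by that visit. At the other post-baseline visits, start Expected from treated subjects in place of all those screened. Completed, Withdrawn and Missed can keep their present definitions, and the companion table formats should be checked for agreement.

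The touch-up condition needs one sentence in the SAP and one programming condition; the change of base is an edit to the same definition. No endpoint, analysis population or study procedure changes, and there is no evident downside. Any non-zero Missed count at 4a or 4b would then be a real missed visit.
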